9.9.3 Cisplatin

Prior to each cisplatin infusion the following criteria should be fulfilled:

- Leucocytes $\geq 3.5 \times 10^9/L$ or neutrophils $\geq 1.5 \times 10^9/L$
- Platelets $\geq 100 \times 10^9/L$
- Creatinine $\leq 1.5 \text{ mg}/100\text{ml}$
- Urea $< 25\text{mg}/100\text{ml}$

If the above mentioned criteria are not fulfilled at the planned day of infusion, chemotherapy will be delayed until the criteria are fulfilled. If the chemotherapy is delayed, the IMP (CetuGEX™ or cetuximab) administration may not be withheld and needs to be continued with weekly infusions as scheduled. If chemotherapy is delayed for more than 3 weeks (i.e., more than 6 weeks between 2 consecutive Day 1 platinum-based chemotherapy infusions), the chemotherapy will be stopped and the patient will continue with the single-agent maintenance therapy.

The patient's subsequent chemotherapy doses will all be **reduced to 75 % of the initial dose** if any of the following toxicity occurs at any time during a chemotherapy cycle:

- Febrile neutropenia (ANC $< 1.0 \times 10^9/L$, fever $\geq 38.5^\circ\text{C}$)
- ANC $< 0.5 \times 10^9/L$
- Platelets $< 25 \times 10^9/L$
- Non-hematological toxicity grade 3 (NCI-CTC version 4.0): dose may be reduced at the discretion of the investigator

Once a chemotherapy dose modification has occurred, the dosage may not be re-escalated for this patient.

Patients with febrile neutropenia or a delay in therapy due to myelosuppression will be treated with G-CSF on subsequent cycles.

Switching from cisplatin to carboplatin has to be considered if the following toxicity occurs at any time during a chemotherapy cycle:

- Creatinine increase $>$ Grade 1 (NCI-CTC version 4.0)
- Ototoxicity $>$ Grade 2 (NCI-CTC version 4.0)
- Sensory neuropathy $>$ Grade 2 (NCI-CTC version 4.0)

If any of the above mentioned occurs again under carboplatin, chemotherapy has to be discontinued and the patient will enter the single-agent maintenance phase.

For more detailed information, please refer to the SmPCs for cisplatin (Appendix F) and carboplatin (Appendix H).

9.9.4 5-Fluorouracil

Prior to each 5-fluorouracil infusion the following criteria should be fulfilled:

- Leucocytes $\geq 3.5 \times 10^9/L$ or neutrophils $\geq 1.5 \times 10^9/L$
- Platelets $\geq 100 \times 10^9/L$

If the above mentioned criteria are not fulfilled at the planned day of infusion, chemotherapy will be delayed until the criteria are fulfilled. If the chemotherapy is delayed, the IMP (CetuGEX™ or cetuximab) administration may not be withheld and needs to be continued with weekly infusions as scheduled. If chemotherapy is delayed for more than 3 weeks (i.e., more than 6 weeks between 2 consecutive Day 1 platinum-based chemotherapy infusions), the chemotherapy will be stopped and the patient will continue with the single-agent maintenance therapy.

Diarrhea: For patients with grade 3 diarrhea for several days, **a reduction to 80% of the initial dose of 5-FU** is required. If grade 3 diarrhea does recur on a subsequent cycle, then a **further reduction of 20% in the 5-FU dose** is recommended.

Mucositis: For patients with the first episode of mucositis grade 3 lasting several days, **a reduction of the daily dose to 80% of the initial dose of 5-FU** is required. If grade 3 mucositis does recur on a subsequent cycle, then **no further cycle of 5-FU will be given**.

Once a chemotherapy dose modification has occurred, the dosage may not be re-escalated for this patient.

For more detailed information, please refer to the SmPC for 5-FU (Appendix G).

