8.2.2 Exclusion Criteria

A patient will be excluded from the study if the patient meets any of the following criteria:

1. Prior systemic chemotherapy, except if given as part of a multimodal treatment for locally advanced disease which was completed more than 6 months prior to randomization.
2. Cetuximab or other EGFR targeting agent treatment, except if given as part of a multimodal treatment for locally advanced disease which was completed more than 6 months prior to randomization.
3. Surgery (other than minor interventions like diagnostic biopsy or intravenous port implantation) or irradiation within 30 days before randomization.
4. Concomitant anti-tumor therapy or concomitant immunotherapy, live vaccines including yellow fever vaccination (as per cisplatinum Summary of Product Characteristics [SmPC, Appendix F]).
5. Concomitant corticosteroid treatment unless specified within the protocol.
6. Clinical evidence of brain metastasis or leptomeningeal involvement.
7. Patients with nasopharyngeal tumors.
8. Concomitant malignant disease, except for adequately treated tumors with high likelihood of being cured (e.g., basal cell cancer of the skin, cervical cancer or breast cancer in situ). Patients with previous malignancies but without evidence of disease for at least 5 years will be allowed to enter the study.
9. Patients with renal or hepatic impairment (serum creatinine and bilirubin > 1.5 fold above the upper limit of normal ranges, creatinine clearance < 60 ml/min, and transaminase > 5 fold above the upper limit of normal ranges) and patients with hematology parameters outside the normal ranges (hemoglobin < 9 g/dl, absolute neutrophil count < 1500/mm³ and platelet count < 10⁵/mm³) at screening as well as patients with impaired auditory function or platinum-related neuropathy.
10. Clinically active infections \geq Grade 2 using National Cancer Institute (NCI) Common Terminology Criteria for Adverse Events (CTCAE) version 4 and/or requiring intravenous antibiotics.
11. Known active hepatitis B or C.
12. Known human immunodeficiency virus (HIV) infection.
13. Myocardial infarction within 6 months prior to screening.
14. Symptomatic congestive heart failure (New York Heart Association [NYHA] Grade 3 or 4), unstable angina pectoris within 6 months prior to screening, significant cardiac arrhythmia, history of stroke or transient ischemic attack within 1 year prior to screening.

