9.1.2 Non-Investigational Medicinal Products

5-Fluorouracil

The chemotherapy drug 5-FU, a thymidylate synthase inhibitor, will be administered to all patients for the first line treatment phase (a maximum of 6 cycles).

Cisplatin (or, in case of unacceptable toxicity, Carboplatin)

The platinum-salt that will be used in this study is cisplatin. It will be administered as intravenous infusion for the first line treatment phase (maximum of 6 cycles) according to the routine standard of care at each site, avoiding corticosteroids as far as possible. If corticosteroids are required, dexamethasone is to be used (unless contraindicated). Carboplatin may be administered in the same fashion in case cisplatin is not tolerated and dose reduction of cisplatin is not deemed to be the appropriate measure. However, cisplatin is mandatory for the first therapy cycle.

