9.3 Treatments Administered

The treatment period will consist of a first line treatment phase followed by maintenance therapy. CetuGEX™, cetuximab, 5-FU, cisplatin and carboplatin must be administered under the supervision of an investigator experienced in the use of antineoplastic medicinal products. Close monitoring is required during the infusion and for at least 1 hour after the end of the infusion. Availability of resuscitation equipment must be ensured.

Prior to the first infusion of cetuximab, patients must receive premedication with an antihistamine and dexamethasone (or another corticosteroid if dexamethasone is

contraindicated). According to the SmPC¹¹ this premedication is recommended prior to all subsequent infusions of cetuximab.

Prior to the first two infusions of CetuGEX™ (Day 0 and Day 1 of 990mg initial loading dose) patients must receive premedication consisting of paracetamol (acetaminophen) 1 g per os (PO) the evening before the infusion as well as paracetamol 1g PO, dexamethasone (or another corticosteroid if dexamethasone is contraindicated) and antihistamines approximately 60 minutes before the start of infusion. Premedication should be avoided during subsequent cycles. However, premedication might be applied after the occurrence of an IRR in relation to the previous infusion.

During administration of CetuGEX™/cetuximab, IRRs might occur. For a more detailed description of possible IRRs and dose adjustment procedures to be followed in case of IRRs, please refer to Section 9.9.

Combination Treatment Phase

Patients who fulfill all inclusion criteria and do not meet any of the exclusion criteria will be randomized in a 1:1 ratio to receive either CetuGEX™ or cetuximab in combination with 5-FU and cisplatin (or carboplatin later than the first cycle, in case of unacceptable toxicity), for a maximum of 6 chemotherapy cycles.

During the combination treatment phase, even if the chemotherapy is delayed for any reason (e.g., see Sections 9.9.3 and 9.9.4), the IMP (CetuGEX™ or cetuximab) administration may not be withheld and needs to be continued with weekly infusions as scheduled.

CetuGEX™

The study drug CetuGEX™ will be administered as infusion to all patients randomized to the CetuGEX™ arm, once weekly, starting with Day 0. Starting with the second infusion (Day 8 of Cycle 1), a time window of ± 1 day will be allowed for the weekly infusions (calculated from the previous infusion).

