10.1.2 Randomization

If the patient is eligible to participate in this study (i.e., if all inclusion criteria are met and no exclusion criteria apply), the investigator will contact the IWRS for randomization information within 1 to 3 days prior to the next scheduled visit of the corresponding patient. The patient will be randomly assigned to receive either CetuGEX™ or cetuximab by receiving a unique randomization number (as detailed in Section 9.5). The patients do not need to visit the study site for this procedure but can be informed by phone.

Additionally, the pre-existing tissue sample will be sent to the central laboratory for the following analyses:

- EGFR expression by immunohistochemistry at a central laboratory. Further immunohistochemical assessments may be performed on the tumor sample if deemed necessary by the sponsor, e.g. tissue micro arrays to further characterize the tumor.
- p16 tumor suppressor gene status, indicative for high risk of Human Papilloma Virus (HPV) in the tumor (remaining tissue needs to be stored for further analysis in case of eligibility).
- Assessment of HPV status at a central laboratory.

These analyses may be performed at a later time point during the study.

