10.1.3 Combination Treatment Phase

During the combination treatment phase, the patients will receive the study medication (CetuGEX™ or cetuximab) in combination with chemotherapy (cisplatin and 5-FU) for a maximum of 6 cycles of combined treatment. In case of toxicity of cisplatin, carboplatin may substitute cisplatin, but after completion of the first cycle at the earliest.

During the combination treatment phase, even if the chemotherapy is delayed for any reason (e.g., see Sections 9.9.3 and 9.9.4), the IMP (CetuGEX™ or cetuximab) administration may not be withheld and needs to be continued with weekly infusions as scheduled. Additionally, all assessments related to the weekly administration of CetuGEX™/cetuximab should be performed as scheduled (see *). Only assessments relevant for the determination of whether the patient is eligible to continue the chemotherapy treatment (i.e., vital signs measurements and safety laboratory tests) have to be repeated in relation to the next administration of chemotherapy (see also Schedule of Events, Section 18.1).

If the administration of CetuGEX™ or cetuximab is skipped for any reason (see Sections 9.9.1 and 9.9.2), e.g., on Day 8, all assessments scheduled for this study visit

day are to be performed as planned (i.e., including collection of blood samples for the determination of ADA and pre-dose samples for PK).

Table 10-1 displays the ideal treatment schedule for the combination treatment phase.

Table 10-1: Ideal treatment schedule – combination treatment phase

Treatment cycle	Week	Chemotherapy ^a	IMP ^{b,c}	
1	Week 1	D1 ^d D2 – D4	D1	
	Week 2		D8	
	Week 3		D15	
2	Week 4	D1 ^d D2 – D4	D1	
	Week 5		D8	
	Week 6		D15	
3	Week 7	D1 ^d D2 – D4	D1	
	Week 8		D8	
	Week 9		D15	
4	Week 10	D1 ^d D2 – D4	D1	
	Week 11		D8	
	Week 12		D15	
5	Week 13	D1 ^d D2 – D4	D1	
	Week 14		D8	
	Week 15		D15	
6	Week 16	D1 ^d D2 – D4	D1	
	Week 17		D8	Start of maintenance phase
	Week 18		D15	

a) If the chemotherapy is delayed, the IMP (CetuGEX™ or cetuximab) administration needs to be continued with weekly infusions as scheduled.

b) Starting with the second IMP infusion (Day 8 of Cycle 1), a time window of ± 1 day will be allowed for the weekly infusions (calculated from the previous infusion).

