10.3.6.1 Laboratory Safety Assessments

Samples for the following laboratory tests will be collected at the time points specified in the schedule of events (Section 18.1).

Standard Laboratory Assessments

Hematology	White blood cell (WBC) with differential (neutrophils, lymphocytes, monocytes, eosinophils and basophils), hematocrit, hemoglobin, mean corpuscular volume, platelet count, red blood cell (RBC) count
Blood Chemistry	Albumin, total bilirubin, total protein, alanine aminotransferase (ALT), aspartate aminotransferase (AST), glucose, sodium, potassium, chloride, calcium, magnesium, creatinine, creatinine clearance, lactate dehydrogenase (LDH), gamma-glutamyl transferase (GGT), alkaline phosphatase (AP), urea/blood urea nitrogen (BUN)
Coagulation Panel	Prothrombin time (PT), partial thromboplastin time (PTT), fibrinogen
Urinalysis	pH, blood, glucose, protein, ketones
EGFR	EGFR expression from pre-existent tumor tissue sample
p16	p16 tumor suppressor gene status, indicative for high risk of HPV in the tumor (from pre-existing tumor tissue sample)
Pregnancy Test (serum or urine)	Females of childbearing potential only

The safety laboratory tests as mentioned above will be performed at the study site (local laboratory). The assessment of EGFR expression and HPV and p16 status will be performed at the central laboratory. The pre-existing tissue sample will be sent to the central laboratory once the patient was randomized. The analysis of the status will be performed during the conduct of the study, but is no requirement for patient inclusion or randomization. Storage and shipment of tumor tissue samples will be performed according to the instructions of the laboratory.

Blood samples will be taken in accordance with local laboratory standard procedures and as detailed in the laboratory manual where applicable.

Specimen Handling Requirements

The transmission of infectious agents may occur through contact with contaminated needles and blood or blood products. Consequently, appropriate blood and body fluid precautions should be employed by all study personnel involved in the collection of blood and handling of specimens in both the clinic and laboratory settings. Refer to current recommendations of the appropriate authorities.

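### The urea limit before every cisplatin infusion (Protocol 9.9.3) has no counterpart at entry and no urea nitrogen equivalent, so platinum can be held in an eligible patient at one site and given at another

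*Protocol*

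**What the plan says.** **Dosing rule.** Protocol 9.9.3 introduces its conditions with "Prior to each cisplatin infusion the following criteria should be fulfilled". They cover leucocytes or neutrophils, platelets, creatinine (at most 1.5 mg/100 ml) and urea (below 25 mg/100 ml). No cycle is exempt. The consequence is binding: "If the above mentioned criteria are not fulfilled at the planned day of infusion, chemotherapy will be delayed until the criteria are fulfilled". Meanwhile the antibody "administration may not be withheld and needs to be continued with weekly infusions as scheduled" (Protocol 9.3, repeated in 9.9.3).

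**Platinum choice in cycle 1.** Protocol 9.1.2: "However, cisplatin is mandatory for the first therapy cycle". Protocol 10.1.3: "carboplatin may substitute cisplatin, but after completion of the first cycle at the earliest".

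**Entry.** Exclusion criterion 9 (Protocol 8.2.2) limits "serum creatinine and bilirubin > 1.5 fold above the upper limit of normal ranges", creatinine clearance, transaminases, hemoglobin, neutrophils and platelets. Neither it nor any other entry criterion names urea or BUN. Under Protocol 10.1.2 a patient is randomized "if all inclusion criteria are met and no exclusion criteria apply".

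**Measurement.** Protocol 10.3.6.1 lists "urea/blood urea nitrogen (BUN") as one chemistry item, run at the site's local laboratory. Protocol 7.3 plans about 40 sites in Europe and the USA. SAP 10.2 converts biochemistry to SI units, but for analysis only, not for dosing.

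**5-FU.** Protocol 9.9.4 gives 5-FU its own conditions, on blood counts only, with no renal item.

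**The concern.** Two gaps meet at the same rule.

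First, a patient can satisfy every entry criterion, be randomized, and then fail the urea condition on the first chemotherapy day. The antibody goes ahead, cisplatin does not, and carboplatin is not available until cycle 1 is complete. That patient starts without the platinum backbone that both arms are meant to share, and rightly stays in the intention-to-treat analysis.

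Second, the limit is given for one analyte on one scale, while the laboratory panel accepts either of two analytes whose mass values differ by more than a factor of two. If some sites compare a BUN result with 25 and others compare urea with 25, the reporting convention of the local laboratory decides whether platinum is given. This can recur at each of up to six cycles.

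What is at stake is delivery of the combination regimen and its consistency across sites.

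**Working it through.** The plan has no figure of its own to reproduce here. The check sets the entry and dosing limits side by side and then converts units.

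**Step 1. Does each dosing-day condition have an entry counterpart?**

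| Item | Entry (8.2.2, criterion 9) | Before cisplatin (9.9.3) | Match |
|---|---|---|---|
| Neutrophils | excluded if < 1500/mm³ | ≥ 1.5 × 10⁹/L (or leucocytes ≥ 3.5 × 10⁹/L) | same neutrophil value |
| Platelets | excluded if < 10⁵/mm³ | ≥ 100 × 10⁹/L | same value |
| Creatinine | relative to upper normal limit, plus a clearance limit | ≤ 1.5 mg/100 ml | near counterpart, different scale |
| Urea | none | < 25 mg/100 ml | none |

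Urea is the only measured quantity in the cisplatin list that the entry criteria do not address.

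**Step 2. Convert the limit.** Inputs: 25 mg/100 ml (250 mg/L) from Protocol 9.9.3; molar mass of urea 60.06 g/mol, of which nitrogen is 28.01 g/mol. The molar masses are chemical constants and are not in the documents.

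- Mass ratio of urea to urea nitrogen: 60.06 / 28.01 = 2.144.
- Limit read as urea: 250 / 60.06 = 4.16 mmol/L; equivalent BUN = 25 / 2.144 = 11.7 mg/100 ml.
- Limit compared with BUN: 250 / 28.01 = 8.9 mmol/L; equivalent urea = 25 × 2.144 = 53.6 mg/100 ml.

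A patient with urea from 25 to just under 53.6 mg/100 ml (BUN from 11.7 to just under 25) is held under one reading and treated under the other.

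**Step 3. Compare with a normal range.** The documents give none. Assumption: the upper normal limit of urea is 40 to 45 mg/100 ml.

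- In mmol/L: 400 / 60.06 = 6.7 and 450 / 60.06 = 7.5.
- Literal limit as a share of the upper normal limit: 25 / 45 = 56% and 25 / 40 = 63%.
- Limit compared with BUN: 53.6 mg/100 ml urea, above both 40 and 45.

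Under this assumption the literal rule holds some patients whose urea is normal, and the BUN reading holds none of them. Steps 1 and 2 do not depend on the assumption.

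**Step 4. What can be said about frequency?** Nothing. The documents contain no distribution of urea and do not say which sites report which analyte.

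**The case against.** The strongest reply is that 9.9.3 already names the analyte and the unit. The laboratory list gives urea and BUN as alternatives, not as synonyms, so a site holding a BUN result should convert it, and the 2.14-fold gap appears only if it does not. That is correct on the face of the text. What remains is that the protocol text offers no converted value, and that the literal reading has its own problem under the normal-range assumption. The cisplatin SmPC (Appendix F) and the laboratory manual are separate documents and might hold guidance; this point is limited to the protocol text.

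A dosing-day check separate from entry is also ordinary practice. Entry already has creatinine and clearance limits, urea can change within the 28-day screening window, and exclusion 16 lets the investigator keep out a patient with an interfering disorder. All of this stands, but none of it sets a urea limit or helps a patient whose usual urea is above 25.

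Several stronger readings are tempting and are not supported:

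- **That all chemotherapy is withheld.** 9.9.3 speaks of chemotherapy being delayed, but 9.9.4 gives 5-FU criteria that a urea failure does not breach. The text leaves it open whether 5-FU proceeds.
- **That a patient held at cycle 1 loses chemotherapy after 3 weeks.** The stopping rule is explained by the gap between two consecutive Day 1 infusions, which does not fit a first infusion not yet given.
- **That the 3-week allowance measures the harm.** It is a maximum permitted delay, not an expected one, and says nothing about an effect on PFS.

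**Conclusion.** The point holds as a defect in a dosing rule. Followed literally, 9.9.3 can hold platinum in a patient who met every entry criterion, with no carboplatin option in cycle 1. A site comparing BUN with 25 would treat the same patient. The two readings are 4.2 and 8.9 mmol/L of urea, a 2.14-fold difference that rests only on molar masses. The statement that the literal limit catches patients with normal urea rests on the assumed upper normal limit of 40 to 45 mg/100 ml.

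The number of patients affected is unknown. A reader might infer bias for or against CetuGEX, but the documents do not support that: the same limit and the same consequence apply in both arms. The harm is delayed chemotherapy and inconsistent dosing across sites. Randomization, the primary test, the significance level and the sample size are untouched.

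**What to change.** 1. Have the sponsor's clinical team confirm whether 25 mg/100 ml is meant as urea or as urea nitrogen.
2. State the confirmed limit in 9.9.3 for both analytes, in mg/100 ml and mmol/L. If urea nitrogen is meant: BUN < 25 mg/100 ml, equal to urea < 53.6 mg/100 ml or 8.9 mmol/L. If urea is meant: urea < 25 mg/100 ml or 4.2 mmol/L, equal to BUN < 11.7 mg/100 ml.
3. Check the confirmed 9.9.3 limits on the latest screening chemistry before the IWRS call.
4. State whether 5-FU proceeds when only the cisplatin renal criteria fail.

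Two remedies are not recommended. A literal entry exclusion at urea 25 mg/100 ml would, under the same assumption, bar patients with normal urea. Applying the urea limit only from cycle 2 would remove a renal check before the first 100 mg/m² dose of cisplatin. If the team confirms the literal urea value, it should justify that value before using it in step 3.

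The cost is protocol wording; urea/BUN is already in the screening chemistry, so no new test is needed. The downside of step 3 is slightly narrower entry. Because chemistry is repeated before dosing, failures on the day are reduced, not removed.

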9.10 Drug Accountability

Shipment of study medication will be performed by Glycotope GmbH or an authorized delegate including a shipment record and approval form. Each delivery of study medication must be inspected and acknowledged by an authorized team member of the study personnel and must be kept in a secure locked location only accessible by authorized study personnel.

Clinical supplies are to be dispensed only in accordance with the study protocol. Dispensing of study medication to the patients must be recorded on drug accountability logs and in the eCRF.

The inventory will be available to the monitor to verify the drug accountability during the study. Any unused bottles will be returned to Glycotope GmbH or its designee or can be destroyed at the study site upon sponsor's request after the drug accountability check has been performed. Empty or partially used bottles must not be returned and should be destroyed at the study site following local policies, after the monitor has reviewed the remaining volumes versus the eCRF and accountability records.

